7 SAFETY ASSESSMENTS

7.1 Specification of Safety Parameters

Refer to section 7.4, DSMB.

7.2 Methods and Timing for Assessing, Recording, and Analyzing Safety Parameters

Refer to section 7.4, DSMB.

7.3 Adverse Events and Serious Adverse Events

The risks of participating in this study involve the potential for becoming upset, psychologically stressed or fatigued, and potential loss of confidentiality. Subjects may experience discomfort when discussing health or worries. A trained facilitator will be available to discuss any questions or concerns about ACP. If concerns that are distressing come up in the course of facilitation discussions or any adverse events occur, facilitators will provide this information to primary care providers and provide contact information for participants to discuss any distressing issues. As with all standard care, patients and families may decide to stop ACP facilitation at any time.

It is possible that some persons and family members who choose to have an ACP conversation with the ACP facilitator may become upset or experience discomfort by responding to questions about wishes for future medical care, by participating in agenda setting or ACP discussions. ACP is an accepted standard in clinical care where benefits outweigh risks, and we will institute several accepted mechanisms to reduce the potential for psychological discomfort. SHARING CHOICES facilitators will receive training in techniques for approaching persons, including those with ADRD and family members, about ACP. Additional training in sensitivity to discussing topics related to ACP and cultural competency for working with diverse populations where there may be specific needs for these discussions will be required.

- As with all standard care, ACP is voluntary for patients, and ACP sessions will only be initiated or terminated at the direction of the patient.
- While it is possible that agenda setting or ACP may introduce tension in the person-family relationship by acknowledging the distinct perspective of each individual, extensive research has also found significant benefits with these discussions, and facilitators will be trained to anticipate concerns and mediate difficult discussions.
- Family of older persons with significant health conditions, including those with Alzheimer's Disease and Related Dementias, are at heightened risk of depression and anxiety. Should this come up as an issue, the facilitator will ask the family if they would like an educational brochure about depression or anxiety (as

- appropriate), and encourage them to follow up to discuss this with their clinician.
- In the event of extreme psychological discomfort among patients or families in ACP discussions, facilitators will be trained in procedures for ensuring necessary medical or professional referrals. We will identify appropriate referral resource(s) for distressed family members. Primary care patients will be referred to their primary care clinician. Family will be referred to the health system referral resource or to medical or psychological care (e.g., counseling, support, advocacy) as appropriate.

7.4 Safety Monitoring

The Data and Safety Monitoring Board (DSMB) will act in an advisory capacity to the National Institute of Aging (NIA) Director to monitor participant safety, data quality and evaluate the progress of the study. The DSMB will be responsible for reviewing the safety of study participants during the conduct of this study and provide recommendations to the research team on specific aspects of the research protocol as it pertains to safety, potential study alerts and adverse events.

The DSMB includes experts in or representatives with familiarity in the conduct of clinical trials with older adults from the fields of:

- Relevant clinical expertise,
- Clinical trial and research methodology, and
- Biostatistics.

The DSMB responsibilities are to:

- Review the research protocol, informed consent documents and plans for data safety and monitoring;
- Provide periodic and independent review of study procedures including enrollment progress;
- Evaluate the progress of the trial and appropriateness of trial procedures, including periodic assessments of data quality and timeliness, recruitment, accrual and retention, participant risk versus benefit, performance of the trial sites, and other factors that can affect study outcome;
- Review adverse events (AEs) including serious events and offer recommendations regarding the trial based on such observed events;
- Review study performance, make recommendations and assist in the resolution of problems reported by the Principal Investigator;
- Protect the safety of the study participants;
- Report to NIA on the safety and progress of the trial;
- make recommendations to the NIA, the Principal Investigator, and, if required, to the Food and Drug Administration (FDA) concerning continuation, termination or other modifications of the trial based on the observed beneficial or adverse effects of the treatment under study;
- If appropriate, review interim analyses in accordance with stopping rules, which are clearly defined in advance of data analysis and have the approval of the DSMB;
- Ensure the confidentiality of the study data and the results of monitoring; and,

- Assist the NIA by commenting on any problems with study conduct, enrollment, sample size and/or data collection.

Any DSMB member who develops a conflict of interest during the course of the trial will be asked to resign from the DSMB and another person with similar areas of expertise will be sought. Otherwise, DSMB membership is to be for the duration of the trial. The DSMB will discharge itself from its duties when the last participant completes the study.

8 INTERVENTION DISCONTINUATION

As with usual clinical care, the facilitator will stop ACP discussions whenever the patient or family chooses not to participate.

9 STATISTICAL CONSIDERATIONS

9.1 General Design Issues: N/A.

9.2 Sample Size and Randomization

The unit of randomization for this study is the primary care practice. Practices will be stratified by health system and balanced on practice characteristics, including practice size, geographic location (urban, rural, suburban), and patient mix by race.

Practices randomized to control will continue to provide usual care. Practices randomized to SHARING CHOICES will provide usual care as well as the components of SHARING CHOICES. SHARING CHOICES will be available to all patients ages 65 and older who receive care at up to 33 practice sites.

9.3 Interim analyses and Stopping Rules: N/A.

9.4 Outcomes will include the rates of advance directive documents uploaded to the EHR (primary outcome), advance care planning documentation, and potentially burdensome care within the last six months of life.

9.5 Data Analyses

We will compare SHARING CHOICES and control practices by analyzing the distribution of practice-level characteristics at baseline using appropriate graphical procedures, summary statistics, and multivariate methods. We will examine consistency of effects stratified by patient age group, gender, race, ADRD diagnosis, and primary care practice. We will compute the effect size of outcomes to assess SHARING CHOICES effects relative to published treatment effect estimates for ACP.

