6 STUDY PROCEDURES

Audit

Preparatory to the detailed audit, an exploratory analysis will be performed using Natural Language Processing (NLP) to determine the number of existing patient records with a textual reference to advance care planning processes and documentation. This analysis will not include patient identifiers. NLP will be used to identify the proportion of patients whose charts do and do not have official documentation of an advance directive (e.g., documentation of a named health care agent or completion of a living will) and/or MOLST/MOST who also have a textual reference to advance care planning-related conversations or documentation in the clinicians' note. Results will be examined in the aggregate by clinic site. We seek to understand the percentage of patients at each clinic who have engaged in an ACP-related encounter by whether they do or do not have documentation of their wishes.

For each of the 19 JHCP and 35 MedStar Health clinics that are part of this trial, we will randomly select 30 - 40 electronic health records of patients age 65 and older under the care of a clinician at the clinic for whom an advance directive has been documented in the electronic health record. Trained study staff at JHCP and MedStar Health will manually review the documented advance directive to confirm that the uploaded document is an advance directive, and, if so, whether the advance directive includes the naming of a health care agent only, the completion of a living will only, or both. The goal of the advance directive audit will be to identify the percentage of advance directives that are documented as being completed that are in fact an advance directive. We will additionally identify variability in the accuracy of advance directive completion by clinic, by patient age group, and for patients with and without a diagnosis of dementia.

Mailings

PHI from EPIC will be requested and disclosed to School of Public Health team members to access data on patients who may be eligible for the advance care planning services – this data will include name, age, primary care physician, upcoming appointments, and address. The team members will use this to identify patients who can receive the SHARING CHOICES intervention (over 65 and with an upcoming appointment in primary care clinics randomized to SHARING CHOICES) and will use patient names and addresses in order to mail the information about the SHARING CHOICES components available in their clinic.

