Outcomes from practices randomized to SHARING CHOICES will be compared to practices within the same system who are randomized to usual care. Outcomes will be assessed at the level of the practice. Control practices will continue to deliver their usual care practices with respect to ACP and agenda setting.

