10 DATA COLLECTION AND QUALITY ASSURANCE

10.1 Data Collection

No data will be collected; all data will be secondary analyses of data collected for routine clinical care. Health information technology staff will extract outcome measures of ACP documentation, advance directive documentation, portal registration, and potentially burdensome end-of-life care from the patient electronic health record. Data extracted will also include demographics, insurance type, diagnoses, potentially burdensome end-of-life care (e.g. hospitalizations, emergency department visits), deaths, advance directive documentation, advance care planning documentation, and uptake of patient and family portal registration and use. All data are routinely recorded as part of routine clinical care and available in the EHR and from the Maryland-DC CRISP health information exchange.

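### Section 9.5 plans treatment effects by individual practice, which a practice-randomised trial cannot estimate, and gives no method for the within-system, practice-level comparison set elsewhere

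*Combined protocol and SAP*

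**What the plan says.** On randomisation, section 9.2 says "The unit of randomization for this study is the primary care practice". Practices are "stratified by health system and balanced on practice characteristics, including practice size, geographic location (urban, rural, suburban), and patient mix by race".

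On the comparison, section 6 (Outcomes) says that outcomes from SHARING CHOICES practices "will be compared to practices within the same system who are randomized to usual care", and that "Outcomes will be assessed at the level of the practice". The synopsis (Design and Outcomes) also puts the analysis at practice level.

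On analysis, the methods named in section 9.5 concern baseline only: "analyzing the distribution of practice-level characteristics at baseline using appropriate graphical procedures, summary statistics, and multivariate methods". The section then turns to subgroups: "We will examine consistency of effects stratified by patient age group, gender, race, ADRD diagnosis, and primary care practice". For outcomes it adds only that an effect size will be computed and set against published estimates.

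On data, section 10.1 says "Health information technology staff will extract outcome measures of ACP documentation, advance directive documentation", among other fields. Section 10.2 says that individual practices will not be identified.

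**The concern.** A consistency analysis compares the treatment effect across strata, so each stratum needs patients or practices from both arms. Age group, gender, race and ADRD diagnosis meet that condition. A single practice does not. A table of results by practice would show how practices differ from one another for any reason, and could be misread as evidence on whether the intervention works consistently.

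The second matter is smaller. The plan fixes the unit of analysis and the within-system comparison, but section 9.5 does not say how that comparison is made or whether a baseline rate is used. With a few dozen randomised units, precision that costs almost nothing is worth having. Fixing the model before outcomes are seen also closes an avoidable choice.

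**Working it through.** **Inputs from the documents.** The clinics number 19 JHCP + 35 MedStar = 54 (sections 3 and 6). The ceiling is 100 practices (synopsis, section 3), with at most 33 SHARING CHOICES sites (section 9.2). No alpha, target effect, between-practice SD, baseline correlation, system gap or allocation ratio is given, so there is no stated power to reproduce.

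**Step 1: can the effect be estimated?** Take 54 practices, each wholly in one arm. The result is the same with 27 or with 33 treated.
- Practices containing both arms: 0 of 54.
- Practice indicators plus treatment: 55 columns, rank 54, so treatment is aliased with practice.
- Practice plus practice-by-treatment: 108 columns, rank 54, so no practice-specific effect exists.
- Treatment by age group, and treatment by health system: 4 columns, rank 4, so both can be estimated.

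**Step 2: illustrative power.** This is not the trial's power. Assumptions: two-sided 5%, effect d in between-practice SD, practices weighted equally, no system gap.

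Unadjusted power uses the noncentral t with noncentrality d / √(1/n₁ + 1/n₂) and n₁ + n₂ − 2 degrees of freedom.
- 27 v 27, d = 0.5: 0.5/√(2/27) = 1.837, 52 df, power 0.438.
- 33 v 21, d = 0.5: 1.791, 52 df, power 0.420.
- 33 v 67, d = 0.5: 2.351, 98 df, power 0.644.

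Adjusted power was simulated (error about 1 point) with arms randomised within system and the model arm + system + baseline. Here r is the baseline/follow-up correlation, so the residual SD shrinks by √(1 − r²). The 33 v 67 row assumes systems of 35 and 65 practices.

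| Split, d | Unadjusted | r = 0 | 0.3 | 0.5 | 0.7 | 0.8 |
|---|---|---|---|---|---|---|
| 27 v 27, 0.3 | 19% | 18% | 20% | 24% | 32% | 43% |
| 27 v 27, 0.5 | 44% | 43% | 46% | 54% | 70% | 84% |
| 27 v 27, 0.7 | 71% | 70% | 75% | 82% | 94% | 98% |
| 33 v 21, 0.5 | 42% | 41% | 45% | 52% | 68% | 83% |
| 33 v 67, 0.5 | 64% | 64% | 68% | 76% | 90% | 97% |

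**Step 3: the system term.** For 27 v 27 and assumed gaps between systems of 0, 1 and 2 clinic SD, a test that omitted system would have type I error of 5.0%, 2.9% and 0.9%. With the term it is 4.8% to 5.1% at every gap. Omission makes the test conservative; it does not create false positives.

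**Step 4: what interactions can show.** With 9 of 19 and 18 of 35 clinics treated, the treatment-by-system standard error is √(1/9 + 1/10 + 1/18 + 1/17) = 0.571 SD. For 80% power the effects in the two systems must differ by about 1.63 SD. With baseline at r = 0.7 the standard error is 0.571 × √(1 − 0.49), about 0.407, and the difference about 1.16 SD.

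**The case against.** **The phrase may be loose wording.** It may mean practice characteristics or practice type (section 4 lists internal, family and geriatric medicine). Because section 10.2 says practices will not be identified, published practice-by-practice effects are unlikely. This is fair, and the primary comparison is unaffected. But section 9.5 does not say what is meant, so the correction is still needed.

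**The health-system stratum is not ignored.** A reader might infer from section 9.5 that stratification is dropped at analysis. The documents do not support that, since section 6 commits to comparing practices within the same system. Only the method is missing. The conservative figures in Step 3 describe an analysis that the plan does not propose.

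**Clustering is not ignored either.** A reader might infer that, with no model named, a patient-level test with inflated error is planned. The synopsis and section 6 fix the practice as the unit of analysis, which avoids that.

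**Baseline adjustment is an option, not a requirement.** This stands. At r of 0 to 0.3 it moves power only from 44% to between 43% and 46%. Nor does the planned audit supply the covariate. Its manual review samples only patients who already have a documented AD. The text-search step, of which section 6 says "Results will be examined in the aggregate by clinic site", is not described as giving the AD rate from the outcome field. Section 2.2 adds that the accuracy of AD documentation at the two systems is not yet well understood, which bears on r.

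**Conclusion.** The by-practice item is wrong as written: no practice contains both arms, so its effect cannot be estimated under any split. That rests on section 9.2 alone and needs no assumption.

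The modelling point is a cheap improvement, not an error that biases the result. At 27 v 27 and 0.5 SD the gain runs from a loss of about 1 point at r = 0 to about 40 points at r = 0.8 (44% to 84%). It depends wholly on r, the effect size and the split, none of which the documents give. The system term implements what section 6 already intends.

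A reader might take the ceiling of 100 practices to mean 50 v 50. The cap of 33 SHARING CHOICES sites in section 9.2 rules that out, so 33 v 67 is the relevant upper case.

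**What to change.** In section 9.5:

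1. Replace primary care practice in the consistency list with the section 9.2 factors: health system, practice size, location and patient race mix. Examine them as exploratory treatment-by-factor interactions with confidence intervals. If practice type is meant, name it.
2. State the primary comparison: a regression of the practice-level AD rate on arm, with a health-system term, the practice's pre-launch AD rate and a t reference. Say whether practices are weighted by size; the figures above weight them equally.
3. Define the pre-launch rate by a dated pull of the same EHR field as the outcome, not from the manual audit.

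The cost is SAP wording, one baseline pull of a field already on the extraction list, and two degrees of freedom, worth about 1 point of power if the baseline rate proves uninformative. The interactions must stay exploratory, because with 54 clinics only very large differences between systems could be detected.

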10 DATA COLLECTION AND QUALITY ASSURANCE

10.1 Data Collection

No data will be collected; all data will be secondary analyses of data collected for routine clinical care. Health information technology staff will extract outcome measures of ACP documentation, advance directive documentation, portal registration, and potentially burdensome end-of-life care from the patient electronic health record. Data extracted will also include demographics, insurance type, diagnoses, potentially burdensome end-of-life care (e.g. hospitalizations, emergency department visits), deaths, advance directive documentation, advance care planning documentation, and uptake of patient and family portal registration and use. All data are routinely recorded as part of routine clinical care and available in the EHR and from the Maryland-DC CRISP health information exchange.

10.2 Data Management

Information extracted from electronic health records will be stored in a database on a secure server (SAFE Desktop). The data will be analyzed and presented only in aggregate at the practice level and individual practices will not be identified. All demographic information will remain confidential. No personal identifiers will be included in the database. The electronic database will be managed by Senior Statistician on the study, [name] who will track and log issuance of analytic datasets, and return/removal when approved use ends. Access to analytic datasets will be subject to conditions established by the PIs and [name]. Electronic analytic datasets will be provided to authorized study personnel with the same data protection requirements established for the study database and can only be used on the secure SafeDesktop (JHCP). Only the PIs, Co-Investigators and research staff will have access to the SafeDesktop that contains study data. The PIs and the research staff are listed in eIRB and have completed the Human Subjects Training.

Patient protected health information (PHI) will be obtained by the Chesapeake Regional Information System for our Patients (CRISP). Death data from the Vital Statistics Agency will be collected by CRISP and used to deliver a de-identified data set for patients who died during the study.

Data will be stored and managed by Johns Hopkins personnel on data storage servers housed at the secure Mt. Washington site. Data will be transferred only to devices accessible to those with credentialed Johns Hopkins University log-in information. Transfer or storage of data will be on encrypted devices with specific user access. Access to patient data will be restricted to authorized study personnel at Johns Hopkins as determined by study PIs, and will include the PIs, Co-Investigators, and select research staff members. All credentialed users will be listed in the eIRB and have completed patient privacy, electronic information security and data management, and health privacy for researchers training. If a patient revokes permission for PHI access, data will be destroyed in accordance with Johns Hopkins University data management policies.

Connection to the data will be completed on SAFE Desktop. If the performance of analytical software is not adequate on the virtual workspace, limited datasets from CRISP will be downloaded from SAFE Desktop and analyzed on the personal workstation of lead

statistician, [name], which is managed by IT@JH (EB-CO-8TTQ2W2 – Note: [name] is in the process of updating his workstation to an IT@JH managed laptop: EB-CO-257ZKS3). Datasets are limited and patients are assigned a unique identifier by CRISP which obfuscates identification by Johns Hopkins or MedStar Health personnel. Downloaded data on the personal workstation will be managed by [name] and accessible only to [name] and [name]. Immediately upon completion of analysis, downloaded data will be deleted. Upon request, a Certificate of Destruction can be made available to memorialize this action.

10.2.1 Data Sharing for Analysis

Data Sharing will be brokered with involvement of the Maryland-DC CRISP health information exchange, and supported by a Data Use Agreement between Johns Hopkins and MedStar Health to share an integrated limited data set that combines de-identified patient-level information from both organizations.

As graphically depicted in Figure 1, Johns Hopkins and MedStar Health will first upload patient-level information regarding candidate patient participants from each respective health systems to CRISP using a secure link that was successfully piloted in the R61 planning phase period. CRISP will assign CRISP IDs that are unique to the health information exchange only. These CRISP IDs, ID mapping instructions, and data extracted from the information exchange for patients who have died will be returned to each respective organization. Hopkins and MedStar will then integrate CRISP IDs with information extracted from their electronic health records that is pertinent to proposed data analyses, such as treatment group, age, gender, race/ethnicity, having a documented advance directive, and for those under the care of a clinician from intervention clinics, date of SHARING Choice mailing(s), and completion of an advance care planning conversation.

Johns Hopkins and MedStar Health data staff will independently create limited data sets using CRISP IDs as identifiers, working with guidance and support of the Johns Hopkins Core for Clinical Research Data Acquisition (CCDA) staff. A CCDA staff member will review and certify each limited data set to ensure that it adheres to standards.

MedStar Health will share a limited dataset with CRISP IDs with Johns Hopkins. Limited datasets for both organizations will be stored and analyzed on SAFE Desktop, following the data safety standards detailed in Section 10.2. [name] will combine the two limited datasets and remove duplicate patients (identified by CRISP IDs, matching across Johns Hopkins and MedStar Health).

[figure not shown]

Figure 1. Data Acquisition, Storage, and Flow for Analysis

